7 STATISTICAL METHODS & DETERMINATION OF SAMPLE SIZE

7.1 Statistical and Analytical Plans

The statistical methods provided in this protocol will be focused on primary and key secondary analyses. Complete and specific details of the statistical analysis will be described in the statistical analysis plan (SAP).

7.2 Definition for Analysis Populations

The intent to treat (ITT) population will consist of all randomized subjects. Subjects will be summarized according to the randomized study drug.

The safety population will consist of all subjects who received at least 1 administration of study drug. Subjects will be summarized according to the study drug actually received.

The PK population will consist of all subjects with evaluable plasma concentrations of AGN-190584.

7.3 Handling Potential Intercurrent Events for the Primary and Key Secondary Endpoints

The following methods will be used to address potential intercurrent events for both the primary and key secondary endpoints:

- Subjects who prematurely discontinued study drug before the Day 14 visit will be considered as nonresponders.
- Subjects who die before assessment of the endpoint will be considered as nonresponders for the endpoint.
- Subjects who are lost to follow-up and are missing data for the endpoint will be considered as nonresponders for the endpoint.

Missing data will be regarded as a nonresponder, for both the primary and key secondary endpoints.

7.4 Statistical Analyses for Efficacy

The efficacy analyses will be conducted on the ITT population based on treatment as randomized. Baseline for efficacy is defined as the last nonmissing efficacy assessment before the first dose of study drug or randomization if no study drug is given. All statistical tests will be 2-sided at a significance level of 0.05. All confidence intervals (CIs) will be 2-sided 95%.

[Summary and Analysis of the Primary Endpoint](#)

The proportion of subjects gaining 3 lines or more in mesopic, high-contrast, binocular DCNVA with no more than 5-letter loss in mesopic CDVA with the same refractive correction at Day 14, Hour 9 will be

summarized by treatment group using the ITT population. As presented in the estimand for the primary efficacy endpoint in Section 3.1, the composite strategy will be used to handle the intercurrent events. Subjects with intercurrent events prior to Day 14 Hour 9 will be considered as nonresponders for the primary efficacy endpoint. Subjects who have missing data for the primary efficacy endpoint will be categorized as nonresponders in the primary efficacy analysis.

The comparison of the proportions between AGN-190584 and Vehicle will be made using the Pearson's chi-square test. The treatment difference will be provided with a 2-sided 95% CI using the normal approximation based on the pooled variance without continuity correction.

Summary and Analysis of Secondary Endpoints

Summary and Analysis of Key Secondary Endpoint

Similar as for the primary endpoint, the proportion of subjects gaining 3 lines or more in photopic, high-contrast, binocular DCNVA with no more than 5-letter loss in photopic CDVA with the same refractive correction at Day 14, Hour 9 will be summarized by treatment group using the ITT population. As presented in the estimand for the key secondary efficacy endpoint in Section 3.1, the composite strategy will be used to handle the intercurrent events. Subjects with intercurrent events prior to Day 14 Hour 9 will be considered as nonresponders for the key secondary efficacy endpoint. Subjects who have missing data for the key secondary efficacy endpoint will be categorized as nonresponders in the key secondary efficacy analysis.

The comparison of the proportions between AGN-190584 and vehicle will be made using the Pearson's chi-square test. The treatment difference will be provided with a 2-sided 95% CI using the normal approximation based on pooled variance without continuity correction.

Summary and Analysis of Supportive Secondary Endpoints

The supportive secondary endpoints will be analyzed using the same method as described in the analysis of the efficacy endpoints will be described in the SAP.

Subgroup Analysis for Efficacy

The primary and key secondary endpoints will be summarized by age group, sex, race, ethnicity, baseline binocular DCNVA severity, iris color, and emmetropes status.

7.5 Pharmacokinetic Analysis

Pharmacokinetic Parameters

Plasma PK parameters following the first and second doses on Day 1 and Day 14 will be calculated separately using standard Phoenix WinNonlin equations. PK parameters calculated after the first and second dose on Day 1 will include area under the concentration versus time curve from 0 to the end of the dosing interval ($AUC_{0-\tau}$), maximum observed concentration (C_{max}), and time to maximum observed concentration (T_{max}). Additionally, the observed concentration at the end of the dosing interval (C_{trough}), and peak-to-trough ratio will be calculated after the first dose on Day 1.

Steady-state PK parameters calculated after the first and second dose on Day 14 will include $AUC_{0-\tauau,ss}$, $C_{max,ss}$, and $T_{max,ss}$. Additionally, $C_{trough,ss}$ and peak-to-trough ratio will be calculated after the first dose on Day 14. Systemic accumulation will be assessed by calculating the accumulation index (AI) for AUC and C_{max} on Day 14.

Additional PK parameters may be calculated, as necessary.

$AUC_{0-\tauau}$ will be calculated by using the linear-log trapezoidal rule.

Statistical Analyses of Pharmacokinetic Data

Details of the statistical analyses of PK data will be described in the PK analysis plan finalized before database lock.

7.6 Statistical Analyses for Safety

The safety analysis will be performed using the safety population; and subjects are assigned to a treatment group based on the treatment actually received, regardless of the treatment randomized.

An AE will be considered a treatment-emergent adverse event (TEAE) if the AE began or worsened (increased in severity or became serious) on or after the date of the first dose of study drug.

An AE will be considered a treatment-emergent SAE if it is a TEAE that additionally meets any SAE criteria.

The number and percentage of subjects with TEAEs during the study will be tabulated by system organ class and preferred term and by system organ class, preferred term, and severity.

If more than one AE is coded to the same preferred term for the same subject, the subject will be counted only once for that preferred term using the greatest severity and strictest causality for the summarizations by severity and by relationship to study drug.

Summary tables will be provided for subjects with SAEs and subjects with AEs leading to discontinuation of study drug. Listings of all AEs, SAEs, and AEs leading to discontinuation of study drug by subject will be presented.

Adverse events of special interest will be summarized by treatment group and the details will be described in the SAP.

Detailed methods for the analysis of other safety variables will be described in the SAP.

7.7 Overall Type I Error Control

A fixed sequence testing procedure will be applied to control the overall familywise Type I error rate at $\alpha = 0.05$ for the primary and secondary hypotheses sequentially. The hypotheses for primary endpoint and the secondary endpoints will be tested in a sequential order:

- **H1 Primary:** The proportion of subjects gaining 3 lines or more in mesopic, high-contrast, binocular DCNVA with no more than 5-letter loss in mesopic CDVA with the same refractive correction at Day 14, Hour 9 (3 hours after the second dose)
- **H2: Key Secondary:** The proportion of subjects gaining 3 lines or more in photopic, high-contrast, binocular DCNVA with no more than 5-letter loss in photopic CDVA with the same refractive correction at Day 14, Hour 9 (3 hours after the second dose)
- **H3 Supportive Secondary:** The proportion of subjects gaining 2 lines or more in mesopic, high-contrast, binocular DCNVA with no more than 5-letter loss in mesopic CDVA with the same refractive correction at Day 14, Hour 9 (3 hours after the second dose)
- **H4 Supportive Secondary:** The proportion of subjects achieving 20/40 or better in mesopic, high-contrast, binocular DCNVA with no more than 5-letter loss in mesopic CDVA with the same refractive correction at Day 14, Hour 9 (3 hours after the second dose)

If at any step a test fails, the test procedure will stop and no further hypotheses will be tested.

7.8 Sample Size Determination

The sample size calculation was considered for the primary efficacy endpoint, the response of gaining 3 lines or more in mesopic, high-contrast, binocular DCNVA with no more than 5-letter loss in mesopic CDVA with the same refractive correction at Day 14, Hour 9 (3 hours after the second dose).

Assuming a responder rate of 25% in the AGN-190584 group and 7% in the vehicle group, and 5% dropout rate, a sample size of 100 subjects per study drug group will provide greater than 90% power using chi-square test at a 2-sided significance level of 5%.

8 ETHICS

8.1 Independent Ethics Committee/Institutional Review Board (IEC/IRB)

The protocol, informed consent form(s), recruitment materials, and all subject materials will be submitted to the Independent Ethics Committee/Institutional Review Board (IEC/IRB) for review and approval. Approval of both the protocol and the informed consent form(s) must be obtained before any subject is enrolled. Any amendment to the protocol will require review and approval by the IEC/IRB before the changes are implemented to the study. In addition, all changes to the consent form(s) will be IEC/IRB approved.

8.2 Ethical Conduct of the Study

The study will be conducted in accordance with the protocol, Operations Manual, International Council for Harmonisation of Technical Requirements for Pharmaceuticals for Human Use (ICH) guidelines, applicable regulations, and guidelines governing clinical study conduct and the ethical principles that

have their origin in the Declaration of Helsinki. Responsibilities of the investigator are specified in [Appendix B](#).

In the event a significant disaster/crisis (e.g., epidemic/pandemic, natural disaster, conflict/combat) occurs leading to difficulties in performing protocol-specified procedures, AbbVie may engage with study site personnel in efforts to ensure the safety of subjects, maintain protocol compliance, and minimize risks to the integrity of the study while trying to best manage subject continuity of care. This may include alternative methods for assessments (e.g., phone contacts or virtual site visits), alternative locations for data collection (e.g., use of a local lab instead of a central lab), and shipping investigational product and/or supplies direct to subjects to ensure continuity of treatment where allowed. In all cases, these alternative measures must be allowed by local regulations and permitted by IRB/IEC.

8.3 Subject Confidentiality

To protect subjects' confidentiality, all subjects and their associated samples will be assigned numerical study identifiers or "codes." No identifiable information will be provided to AbbVie.

9 SOURCE DOCUMENTS AND CASE REPORT FORM COMPLETION

The investigator is responsible for ensuring the accuracy, completeness, legibility, and timeliness of the data reported. All source documents should be attributable, legible, contemporaneous, original, accurate, and complete to ensure accurate interpretation of data. Clinical site monitoring is conducted to ensure that the rights and well-being of human subjects are protected, that the reported trial data are accurate, complete, and verifiable, and that the conduct of the trial is in compliance with the currently approved protocol, ICH Good Clinical Practice (GCP), and applicable local regulatory requirement(s).

10 DATA QUALITY ASSURANCE

AbbVie will ensure that the clinical trial is conducted with a quality management system that will define quality tolerance limits in order to ensure human subject protection and reliability of study results. Data will be generated, documented, and reported in compliance with the protocol, ICH GCP, and applicable regulatory requirements.

11 COMPLETION OF THE STUDY

The end-of-study is defined as the date of the last subject's last visit.

APPENDIX A. STUDY-SPECIFIC ABBREVIATIONS AND TERMS

Abbreviation	Definition
AE	adverse event
AI	accumulation index
AUC	area under the plasma concentration-time curve
AUC _{0-tau}	area under the plasma concentration-time curve from time 0 to the end of the dosing interval
AUC _{0-tau,ss}	area under the plasma concentration-time curve from time 0 to the end of the dosing interval, steady state
BID	twice daily
CDVA	corrected distance visual acuity
CI	confidence interval
C _{max}	maximum observed plasma concentration
C _{max,ss}	maximum observed plasma concentration, steady state
COVID-19	Coronavirus Disease - 2019
C _{trough}	observed plasma concentration at the end of the dosing interval
C _{trough,ss}	observed plasma concentration at the end of the dosing interval, steady state
DCNVA	distance-corrected near visual acuity
GCP	Good Clinical Practice
IB	Investigator's Brochure
ICH	International Council for Harmonisation of Technical Requirements for Pharmaceuticals for Human Use
IEC	Independent Ethics Committee
IMP	investigational medicinal product
IRB	Institutional Review Board
IOP	intraocular pressure
IRT	interactive response technology
ITT	intent to treat
LASIK	laser-assisted in situ keratomileusis
NEI VFQ-25	25-item National Eye Institute Visual Function Questionnaire
NVPTQ	Near Vision Presbyopia Task-based Questionnaire
OSDI	Ocular Surface Disease Index
OTC	over-the-counter
PCR	polymerase chain reaction

PGIC	global impression of change
PGIS	global impression of status
PICQ	Presbyopia Impact and Coping Questionnaire
PK	pharmacokinetic(s)
PRK	photorefractive keratectomy
PRO	patient-reported outcome
SAE	serious adverse event
SAP	statistical analysis plan
SAR	serious adverse reaction
SARS-CoV-2	severe acute respiratory syndrome coronavirus 2
SUSAR	suspected unexpected serious adverse reactions
TEAE	treatment-emergent adverse event
T _{max}	time to maximum observed concentration
T _{max,ss}	time to maximum observed concentration, steady state
VFA app	Visual Function Assessment application

APPENDIX D. ACTIVITY SCHEDULE

The following table shows the required activities across the study. The individual activities are described in detail in the **Operations Manual**.

Procedure	Screening	Study Days (Visits)																			
		Day 1 (Visit 1)							Day 7 (Visit 2)				Day 14/Early Exit (Visit 3)								
Visit Windows	Days -30 to -1	N/A							± 2 days				± 2 days								
Hours		0	1	3	6	7	9	12	0	1	3	6	7	9	0	1	3	6	7	9	12
Informed consent	✓																				
Contact IRT for subject ID number	✓																				
Iris color assessment	✓																				
Demography	✓																				
Medical and ophthalmic history	✓																				
Prestudy/ concomitant medication query	✓	✓							✓							✓					
NEI VFQ-25 and near vision subscale in the Appendix of Optional Additional Questions ^a	✓																				
OSDI ^b	✓																				
AE query ^c	✓	✓	✓	✓	✓	✓	✓	✓	✓	✓	✓	✓	✓	✓	✓	✓	✓	✓	✓	✓	✓
Vital signs ^d	✓	✓				✓										✓				✓	
Urine pregnancy test ^e	✓	✓														✓					
Dominant eye determination	✓																				
Contact IRT for kit assignment/ randomization ^f		✓																			
PIAQ ^g			✓										✓						✓		
Pupillary reaction to light assessment	✓																				
Perform under mesopic conditions (10 to 11 lux at target)																					
Carry out in the order specified. Different charts must be used for the repeated visual acuity measures within the same day.																					

Procedure	Screening	Study Days (Visits)																				
		Day 1 (Visit 1)							Day 7 (Visit 2)							Day 14/Early Exit (Visit 3)						
Visit Windows	Days -30 to -1	N/A							± 2 days							± 2 days						
Hours		0	1	3	6	7	9	12	0	1	3	6	7	9	0	1	3	6	7	9	12	
Dark adaptation ^h	✓	✓	✓	✓	✓	✓	✓		✓	✓	✓	✓	✓	✓	✓	✓	✓	✓	✓			
Mesopic manifest refraction (distance and near) ⁱ	OD, OS																					
Mesopic, high-contrast CDVA + pupil diameter ^j	OU	OU	OU	OU	OU	OU	OU		OU	OU	OU	OU	OU	OU	OU	OU	OU	OU	OU			
Mesopic, high-contrast DCNVA + pupil diameter ^k	OU	OU	OU	OU	OU	OU	OU		OU	OU	OU	OU	OU	OU	OU	OU	OU	OU	OU			
Mesopic NVPTQ ^l		✓													✓					✓		
Perform under photopic conditions (>251 lux at target):																						
Carry out in the order specified. Different charts must be used for the repeated visual acuity measures within the same day.																						
Photopic manifest refraction (distance and near) ⁱ	OD, OS																					
Photopic high-contrast CDVA + pupil diameter ^j	OU	OU	OU	OU	OU	OU	OU		OU	OU	OU	OU	OU	OU	OU	OU	OU	OU	OU			
Photopic, high-contrast DCNVA + pupil diameter ^k	OU	OU	OU	OU	OU	OU	OU		✓	OU	OU	OU	OU									
Single-item PGIS ^l		✓													✓							
Single-item PGIC ^l															✓							
Visual Function Assessment application (VFA app) ^m		✓													✓							
Slit-lamp biomicroscopy	✓	✓	✓		✓				✓	✓			✓		✓	✓	✓	✓	✓			
Fluorescein corneal staining	✓																					
IOP measurement	✓	✓	✓		✓				✓	✓			✓		✓	✓	✓	✓	✓			

Procedure	Screening	Study Days (Visits)																			
		Day 1 (Visit 1)							Day 7 (Visit 2)				Day 14/Early Exit (Visit 3)								
Visit Windows	Days -30 to -1	N/A							± 2 days				± 2 days								
Hours		0	1	3	6	7	9	12	0	1	3	6	7	9	0	1	3	6	7	9	12
Gonioscopy/angle assessment	✓																				
Dilating drop administration	✓																			✓	
Cycloplegic refraction ⁿ	✓																				
Dilated fundoscopic examination ^o	✓																			✓	
Review inclusion and exclusion criteria	✓	✓																			
PK ^p		✓	✓	✓	✓	✓	✓	✓								✓	✓	✓	✓	✓	✓
Study drug administration ^q		✓			✓				✓							✓	✓		✓		
Drop comfort questionnaire		✓			✓				✓							✓	✓		✓		
Post-Dose Tolerability Assessment ^r		✓			✓				✓							✓	✓		✓		
Study drug dispensing to subject								✓													

Study drug administration:

Hour 0 must be at 8 AM ± 1 hour; Hours 1, 3, and 6 (± 15 minutes) will be measured from the time of the completion of Hour 0 study drug administration. Hours 7 and 9 (± 15 minutes) will be measured from the time of the completion of the Hour 6 dose administration (within 15 minutes). Ocular examinations within each lighting condition (mesopic or photopic) may be grouped together by distance (e.g., all near assessments performed in sequence, and all distance assessments performed in sequence) at the investigator's discretion.

- Near vision subscale includes questions A3 to A5 in the Appendix of Optional Additional Questions. This questionnaire will be completed on paper.
- OSDI will be completed on paper.
- Subjects reporting a headache AE will be provided the supplemental headache AE assessment form.
- Blood pressure and heart rate measured after subject has been at rest (seated) for at least 5 minutes
- WOCBP only
- IRT will be used to dispense medication. Please refer to the IRT manual for additional information.
- Conducted with subject's habitual distance correction.

- h. 5 to 10 minutes in mesopic conditions.
- i. If a subject loses ≥ 1 line (≥ 5 letters) of CDVA or DCNVA compared with Hour 0 of the same study visit at Hour 1 after dosing, a manifest refraction should be repeated under the same lighting conditions.
- j. Conducted with subject's best distance correction. CDVA to be measured binocularly. Pupil diameter must be measured in each individual eye.
- k. Conducted with subject's best distance correction. DCNVA to be measured binocularly. Pupil diameter must be measured in each individual eye.
- l. Conducted with subject's best distance correction
- m. Conducted with subject's best distance correction. Half-eye style trial frames with full field trial lenses only.
- n. Distance, photopic. Minimum 30-minute wait after administration of dilating drops.
- o. Investigator should note if the pupil dilated normally. Minimum 30-minute wait after administration of dilating drops.
- p. Blood collection for PK at selected sites (on Days 1 and 14 at Hours 0, 0.25, 0.5, 1, 3, 6 [pre-dose], 6.25, 6.5, 7, 9, and 12). Collection windows of ± 5 minutes should be used for Hours 0.25, 0.5, 6.25, and 6.5; and collection windows of ± 15 minutes should be used for all other blood collection timepoints. Predose samples must be drawn within 15 minutes of the dosing time.
- q. Hour 0 starts after study drug administration. Second dose should be applied within 15 minutes after Hour 6. Site staff will administer study drug during study visits. Subjects will administer the study drug at home in between visits.
- r. Conducted 5 to 10 minutes post-dosing. Only those who reported ocular discomfort symptom(s) will be further queried on the severity and duration of each symptom.

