To ensure proper VA measurement, different charts should be used at each timepoint and no charts should be used in successive VA measures. This should prevent the memory effect. Please note that VA

worksheets labeled 'mesopic' and 'photopic' can refer to the same chart. When rotating different worksheets ensure rotation extends into both mesopic and photopic worksheets.

The worksheets provided by AbbVie are labeled the same way as the corresponding charts. Section 7.3 contains tables of which VA charts should be used for each VA measure, according to timepoint and lighting conditions. Please refer to these tables for the preferred chart rotations to minimize learning effects. It may help to print this appendix for reference.

Corrected Distance Visual Acuity (CDVA)

1. CDVA is performed with the best distance correction determined by the screening manifest refraction under the corresponding lighting conditions.
2. Trial frames and trial lenses or phoropter (or new monofocal correction or habitual correction IF appropriate – see Section 3.12) should be used if correction is needed per the manifest refraction results. If no correction is needed, complete the CDVA without the trial frames or phoropter.
3. AbbVie will provide 3 double-sided distance charts labeled 23214-1 (Front and Back), 23214-2 (Front and Back), and 23214-3 (Front and Back), found at the bottom right-hand corner of the front side. Charts are similar, only differing in letters.
 - a. Site should refer to Section 7.3 on which chart should be used at each timepoint.
 - b. Use the corresponding CDVA worksheet based on the chart selected.
4. The chart should be mounted on the wall or stable stand (eg, lectern) that is 4 meters away from the subject's eyes and at approximately eye level to the average height of the seated subject.
5. Conduct the CDVA measurement OU:
6. Ask the subject to:
 - a. Read the lowest line visible starting with the middle of the chart.
 - b. If read correctly, count the number of letters and proceed to the next line noting letters correct per line, until 2 or fewer letters can be read correctly on that line, then stop.
 - c. VA score (Snellen equivalent) is the lowest line on which 3 or more letters are read correctly. (Note: it is possible that there is more than one line of 3 or 4 correctly read letters; always record the lowest line as the VA score).

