7.4 Visual Acuity Charts Used for Each Visual Acuity Measure

Table 5. Screening Visit Visual Acuity Charts

Screening Visit	Charts Used:	
VA Measure	Mesopic	Photopic
Manifest Refraction Near	23213-1 Front	23213-1 Back
Manifest Refraction Distance	23214-1 Front	23214-1 Back
CDVA	23214-2 Front	23214-2 Back
DCNVA (Repeated 3x for OU)	23213-2 Front 23213-2 Back 23213-3 Front	23213-3 Back
Cycloplegic Refraction Distance	--	23214-1 Front

Table 6. Day 1 (Baseline), Day 7 (Visit 2), and Day 14 (Exit/Visit 3) Visual Acuity Charts

Day 1 (Baseline) Day 7 (Visit 2) Day 14 (Exit/Visit 3)	Charts Used	
VA Measure	Mesopic	Photopic
Hour 0		
CDVA	23214-1 Front	23214-1 Back
DCNVA	23213-1 Front	23213-1 Back
Hour 1		
CDVA	23214-2 Front	23214-2 Back
DCNVA	23213-2 Front	23213-2 Back
Hour 3		
CDVA	23214-3 Front	23214-3 Back
DCNVA	23213-3 Front	23213-3 Back
Hour 6		
CDVA	23214-1 Front	23214-1 Back
DCNVA	23213-4 Front	23213-4 Back
Hour 7 (1 hour after the second dose)		
CDVA	23214-2 Front	23214-2 Back
DCNVA	23213-1 Front	23213-1 Back
Hour 9 (3 hours after the second dose)		
CDVA	23214-3 Front	23214-3 Back
DCNVA	23213-2 Front	23213-2 Back

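### The preferred chart rotation repeats near and distance chart faces within a visit day, including at the Day 14 Hour 9 endpoint reading, against the Activity Schedule's own rule

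*Protocol*

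**What the plan says.** Protocol Appendix D states the rule twice, once in the mesopic block and once in the photopic block: "Different charts must be used for the repeated visual acuity measures within the same day". Operations Manual 3.15 (Chart Usage) gives a softer form with its reason: "different charts should be used at each timepoint and no charts should be used in successive VA measures. This should prevent the memory effect". The same section describes the chart tables as the "preferred chart rotations to minimize learning effects". It notes that "worksheets labeled 'mesopic' and 'photopic' can refer to the same chart" and asks sites to "ensure rotation extends into both mesopic and photopic worksheets".

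Table 6 in Operations Manual 7.4 sets one rotation for Days 1, 7 and 14. It uses only Front faces under mesopic light and only Back faces under photopic light.

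Supply is eight near charts, counted by side (cards 23213-1 to 23213-4; Operations Manual 3.16), and three double-sided distance charts, counted by card (23214-1 to 23214-3; Operations Manual 3.15).

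The primary and key secondary endpoints (Protocol 3.2 and 3.3) combine near gain and distance loss at Day 14 Hour 9. All four hypotheses in the fixed sequence (Protocol 7.7) use that timepoint.

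On where to find the tables, Operations Manual 3.15 says "Section 7.3 contains tables of which VA charts should be used for each VA measure". Section 7.3 is in fact the OSDI scoring sheet; the tables are under "7.4 Visual Acuity Charts Used for Each Visual Acuity Measure".

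**The concern.** A site cannot obey both the mandatory sentence in Appendix D and the preferred table. A site that follows the sentence has to leave the table, so chart exposure at Hour 9 could differ between sites.

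The exposure is also lopsided in time. The Day 1 Hour 0 faces (23213-1 and 23214-1) have no earlier DCNVA or CDVA reading; at screening they serve only for refraction (Table 5). The Day 14 Hour 9 faces have been read before, once on that same day under the same light. If subjects recall letters, near gain looks larger and distance loss smaller, and both errors favour a response. That could raise the absolute responder rates, including the 7% assumed for vehicle.

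**Working it through.** **Notation.** A face is one side of a card; 1F is card 1 Front, 1B is card 1 Back. Readings are at Hours 0, 1, 3, 6, 7 and 9 (Operations Manual 2.1).

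**Supply.** Near: 4 cards × 2 sides = 8 faces, matching the stated eight. Distance: 3 × 2 = 6 faces.

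**Table 6 as it stands (mesopic; photopic is the same with Back faces).**

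| Hour | 0 | 1 | 3 | 6 | 7 | 9 |
|---|---|---|---|---|---|---|
| Near (23213) | 1F | 2F | 3F | 4F | 1F | 2F |
| Distance (23214) | 1F | 2F | 3F | 1F | 2F | 3F |

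Repeats per lighting condition = readings minus distinct faces. Near: 6 − 4 = 2 (Hour 7 repeats Hour 0; Hour 9 repeats Hour 1). Distance: 6 − 3 = 3 (Hours 6, 7 and 9 repeat Hours 0, 1 and 3).

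**Earlier readings of the Day 14 Hour 9 faces.** Mesopic near face 2F: screening 1 + Day 1 2 + Day 7 2 + Day 14 1 = 6. Distance face, same lighting: 2 + 2 + 1 = 5.

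**Can the rule be met?** Within one lighting condition there are 6 readings for 8 near or 6 distance faces, so yes, if each side counts as a chart. Counted by card it fails, since 4 or 3 cards cannot cover 6 readings. Pooled over lighting there are 12 readings, so at least 12 − 8 = 4 near and 12 − 6 = 6 distance reuses are unavoidable.

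**Proposed rotation.**

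| Hour | 0 | 1 | 3 | 6 | 7 | 9 |
|---|---|---|---|---|---|---|
| Near, mesopic | 1F | 2F | 3F | 1B | 2B | 4F |
| Near, photopic | 1B | 2B | 3B | 1F | 2F | 4B |
| Distance, mesopic | 1F | 2F | 3F | 1B | 2B | 3B |
| Distance, photopic | 1B | 2B | 3B | 1F | 2F | 3F |

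| Property per visit day | Near now | Near new | Distance now | Distance new |
|---|---|---|---|---|
| Repeats within a lighting condition | 2 | 0 | 3 | 0 |
| Least number of other faces between uses | 7 | 4 | 5 | 4 |
| Shortest interval between uses (hours) | 7 | 6 | 6 | 6 |
| Hour 9 face read earlier that day, same light | 1 | 0 | 1 | 0 |
| Hour 9 face read earlier that day, either light | 1 | 0 | 1 | 1 |

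The spacings hold whichever lighting is tested first. No face appears at two adjacent hours, so there is no successive reuse. Earlier readings of the Day 14 Hour 9 near face fall to 1 + 1 = 2. For distance they fall to 2 under the same light but stay at 2 + 2 + 1 = 5 over both lights.

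**Why distance cannot do better.** Six photopic readings without repeats use all six faces, so the mesopic Hour 9 face is also read once under photopic light. That happens either earlier in the day or at Hour 9 itself, which would be successive reuse.

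**Side check on power (Protocol 7.8; SAP 2.4).** Exact power sums the binomial probabilities of all outcomes (x, y) with |z| > 1.96, where z = (x/n − y/n) / √[2p̄(1 − p̄)/n] and p̄ = (x + y)/(2n). With 25% against 7% and n = 100 × 0.95 = 95 per arm it is 94.1%, which reproduces the plan's claim of more than 90%. The added points below are assumptions, equal in both arms:

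| Added to both arms | 95 per arm | 100 per arm, rates × 0.95 |
|---|---|---|
| 0 points | 94.1% | 94.0% |
| 2 points | 91.5% | 91.3% |
| 3 points | 90.1% | 90.0% |
| 5 points | 87.6% | 87.3% |

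With equal rates of 7%, 10% and 12% in both arms, exact type I error at 95 per arm is 4.81%, 5.14% and 5.07%.

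**The case against.** Table 6 already controls part of the risk. No face is used in successive readings, no face crosses lighting conditions within a visit day, same-day reuse is 6 to 8 hours apart, and the baseline and Day 14 Hour 9 readings use different faces. All of that stands, but it does not meet the rule in Appendix D or the requirement in Operations Manual 3.15 for a different chart at each timepoint.

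For distance, the redraw moves the same-day repeat into the other lighting condition and does not remove it. If recall of letters does not depend on lighting, the distance half of each endpoint gains little. This stands. For near acuity, a simpler rotation (mesopic 1F-2F-3F-4F-1B-2B, photopic 1B-2B-3B-4B-1F-2F) also complies and keeps wider spacing (6 faces, 7 hours). Its price is that each Hour 9 near face has been read at Hour 1 under the other light. The proposed rotation gives up spacing to leave the endpoint face unread that day.

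Sharing faces across lighting is not a new practice. Operations Manual 3.15 allows it, and Table 5 already lists a Back face among the mesopic screening charts: "23213-2 Front 23213-2 Back 23213-3 Front".

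A reader might infer that the repeats bias the treatment comparison, inflate type I error or leave the trial underpowered. The documents do not support this. Both masked arms follow the same table, no size for a memory effect is given, and the power rows with added points are hypothetical.

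**Conclusion.** The contradiction is real and falls on the endpoint reading. In each lighting condition Table 6 makes two near and three distance same-day repeats, and both components of the primary and key secondary endpoints at Day 14 Hour 9 are among them. It should be fixed, because the supplied charts can comply within each lighting condition at little cost. The benefit is modest: full for the near Hour 9 reading, within-lighting only for distance.

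The feasibility result rests on two readings of the manual: each side of a card is one chart, and faces may be shared between lighting conditions. The direction of harm assumes that recall exists. A reader might also infer that too few charts were supplied. That is so only if the rule is pooled over both lighting conditions or counted by card, and Appendix D prints it under each lighting heading separately.

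**What to change.** 1. In Appendix D and Operations Manual 3.15, state that the different-chart rule applies within each lighting condition and that each side (Front or Back) of a card counts as one chart. Keep the 3.15 sentence on rotating across mesopic and photopic worksheets; the redraw does this.
2. Replace Table 6 with the rotation above, identical on Days 1, 7 and 14. This keeps Day 7 and Day 14 Hour 9 comparable for the time-matched LOCF (SAP 9.3.3 and 9.4.3) and for the other-timepoint analyses (SAP 9.6).
3. Keep card 23213-4 out of any same-day repeat manifest refraction, so that the near Hour 9 faces stay unread. No distance card can be reserved in this way, because all six faces are in use.
4. Keep each subject on one version of the table for all visits.
5. Editorial: change the four Section 7.3 references for the chart tables (two in Operations Manual 3.15, two in 3.16) to 7.4.

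**Cost.** One table, reissued worksheets, short wording changes in two places and four cross-references; no new charts. Least spacing falls from 7 to 4 faces (near) and from 5 to 4 (distance), and the shortest near interval from 7 to 6 hours. The Hour 6 near faces, now unread that day, will have been read once at Hour 0 under the other light. Each distance Hour 9 face will still have been read at Hour 3 under the other light.
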